# INVESTIGATOR STUDY PLAN – Moms@Home

## V1.0

### 1. TITLE

Development of a Mobile Health Intervention to Improve Blood Pressure Management in Pregnancy (Moms@Home)

### 2. EXTERNAL IRB REVIEW HISTORY

NA

### 3. PRIOR APPROVALS:

NA

### 4. OBJECTIVES

Aim 1: Conduct a pilot randomized controlled trial (RCT) of Moms@Home vs. enhanced standard care (ESC). We will enroll 100 pregnant women (50% from racial/ethnic minority groups) with gestational or chronic HTN to determine whether Moms@Home vs. enhanced standard care (BP monitor, diary) improves HBPM adherence (primary outcome). We will also determine the feasibility, acceptability, and sustainability of the 8-week intervention. Hypothesis 1: Participants in the intervention MOMP@HOME group will have better adherence to HBPM, compared to participants in the control ESC group at 8 weeks.

### 5. BACKGROUND

**Description of the Problem :** Hypertension in pregnancy is highly prevalent, its frequency is increasing in the United States, and accounts for 40% of maternal mortalities in the US. The time required for frequent in-person visits, inadequate counseling, and the asymptomatic nature of hypertension are major barriers to effective blood pressure (BP) control in pregnant women. These issues can be addressed through the use of home BP monitoring (HBPM), which reduces the risk of preventable and devastating clinical events and reduces racial inequities in people who are pregnant. Obstetric societies recommend HBPM for all people who are pregnant with hypertension, but many studies suggest that the rates of counseling for HBPM and uptake are low.

**Significance :** Barriers to blood pressure (BP) control in people who are pregnant can be addressed by home BP monitoring (HBPM), which has multiple advantages over clinic-based BP but is underutilized in people who are pregnant. Improving BP control and reducing health inequities are top national priorities, as the adverse effects of hypertensive disorders in pregnancy are lifelong and convey a 2–8-fold increased risk of cardiovascular disease. Although people who are pregnant are motivated to self-manage BP, barriers to BP control based on clinic-based BP measures include the challenges with mothers having time off from work and costs for frequent visits, lack of information about self-care, and low engagement with in-person clinic visits. Clinic-based BP is a poor surrogate for average daily BP, and HBPM values are superior with regard to reliability and prognostic value for mortality and adverse pregnancy events. By facilitating more timely HTN diagnosis and BP control, HBPM reduces the risk of preventable and devastating clinical events. Adults using HBPM are more likely to take BP medications and have diagnosed, treated, and controlled HTN. Digital health interventions can overcome barriers to HTN management but need to be tested in people who are pregnant with HTN. CareEvolution's MyDataHelps™ (MDH) mobile health application (app) was designed to promote HBPM and facilitate communication between people

## **INVESTIGATOR STUDY PLAN – Moms@Home**

### **V1.0**

and their care teams. Designed by diverse Patient Advisory Groups, MDH's secure health dashboard displays BP data and sends text notification reminders to perform HBPM. The MDH app has been used to support multiple NIH-funded cohorts including the electronic Framingham Heart Study (eFHS), RURAL, MIPACT, and DETECT. In the eFHS, women were more likely than men to enroll in HBPM, with 62% regularly using HBPM through 1 year. In pregnant women, digital health interventions improve patient engagement and health equity while allowing for early detection of pregnancy-related problems and communication with care teams. Digital health also reduces wait times and access barriers based on geography or mobility. Increasing smartphone adoption and validated Bluetooth BP monitors, with ability to transmit data remotely, have made HBPM more accessible.

The most effective self-management interventions, including digital health interventions in pregnancy, are grounded in Social Cognitive Theory and incorporate four primary constructs: training/modeling, self-monitoring, goal setting, and reinforcement. Moms@Home will integrate these constructs to increase self-efficacy and improve BP control.

Storytelling is an evidence-based approach with universal appeal to support behavior change and BP control, especially in racial/ethnic minority groups. Storytelling is based on a rich oral tradition common in Black and Hispanic cultures and appeals to the human affinity for sharing stories. This approach is especially effective at reaching persons of racial/ethnic minority groups if the stories are grounded in shared experiences. Storytelling's effectiveness in changing behavior relates to breaking down cognitive resistance through transportation (absorption in the story) and “homophily” (similarities between the storytellers and participants) to change attitudes, skills, and behaviors. Integration with technology and the care team can sustain behavior change, but input from patients and providers is critical.

## **6. INCLUSION AND EXCLUSION CRITERIA\***

### **Participant inclusion/exclusion:**

Inclusion criteria:

- (1) Age 18-50
- (2) Singleton or multiple pregnancies
- (3) English or Spanish speaking
- (4) Diagnosis of Chronic hypertension (8-26 weeks gestational age) or gestational hypertension (20-26 weeks gestational age)
- (5) A patient of the UMass Memorial Health OB/MFM clinics in Worcester, MA
- (6) Willing to share HBPM data
- (7) Comfortable with the use of smartphones and mobile apps

Exclusion criteria:

- (1) Severe HTN (BP greater than or equal to 160/110mmHg at the enrollment visit)
- (2) Current diagnosis of preeclampsia
- (3) Active substance use
- (4) Serious physical illness or any illness that makes them unable to interact with a smart device
- (5) Enrolled in another HBPM program
- (6) Excluded from study participation by their provider
- (7) Inability to provide informed consent

# INVESTIGATOR STUDY PLAN – Moms@Home

## V1.0

(8) Prisoners

### OB/MFM Provider Inclusion/Exclusion (N=10):

**Inclusion criteria:** OB/MFM providers (attending physicians, residents, advanced practitioners, nurses) involved in caring for RCT participants.

**Exclusion criteria:** Inability to verbally communicate in English.

### 7. STUDY-WIDE NUMBER OF SUBJECTS

NA

### 8. STUDY-WIDE RECRUITMENT METHODS

NA – this is not a multi-site study.

### 9. STUDY TIMELINES

Duration of an individual subject's participation in the study: 8 weeks

Duration of the post-study focus groups is estimated to be 1-1.5 hours

Duration anticipated to enroll all study subjects: 1.5 years, longer if not meeting recruitment goals.

Estimated timeline for investigators to complete this study: 2 years

### 10. STUDY ENDPOINTS

#### Aim 1:

##### Primary outcome measures:

- Home Blood Pressure Monitoring (HBPM) adherence at 8 weeks
- Feasibility of Moms@Home – assessed through post-intervention focus groups (intervention group only)
- Acceptability of Moms@Home – assessed through the End-user Mobile Application Rating Scale survey administered at 8 weeks, and the post-intervention focus groups (intervention group only)

##### Secondary outcome measures:

- Engagement with the Moms@Home mobile app will be measured by number of logins, time spent in the app, and storytelling videos watched (4, 8 weeks)
- BP measures - HBPM measures will be gathered from the Moms@Home app and paper BP diaries. Electronic health record review will be used to determine clinic BP values
- Medication adherence – change in medication adherence will be assessed through a brief survey (baseline, 4, 8 weeks)
- Goal attainment scaling - goal attainment will be rated using a 5-point goal attainment scale (baseline, 8 weeks)
- Physical activity - change in physical activity will be tracked by the FitBit (baseline, 4, 8 weeks)
- Moms@Home app sustainability measured with a short sustainability survey (4, 8 weeks)
- Healthcare utilization measures (ex. # of clinic visits, ED visits, admissions) and clinical outcome measures (ex. gestational age at delivery, preeclampsia) (baseline, 4, 8 weeks)
- Self-efficacy measure using the self-efficacy for hypertension questionnaires (baseline, 4, 8 weeks)

Primary safety endpoints

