Participant data will be collected at baseline (study entry) and the 8-wk follow-up in the privacy of the OB/MFM office (before or after clinic visits). Participants will be asked about their age, ethnicity/race, medication use, baseline HBPM use, and health literacy. If the 8-wk follow-up cannot be scheduled in person, this will be conducted over the phone or over Zoom. All 4-week follow-up visits will be done through a phone check-in. Study staff responsible for outcome assessment will be blinded to group assignments. Assessments will be pre-tested to ensure the time burden does not exceed 30 minutes.

**Post-intervention focus group:** After completing the 8-wk pilot test, three participant focus groups (intervention arm only, N=5/group, 1–1.5-hours) will discuss their experience and barriers/facilitators to engagement with Moms@Home.

Two focus groups with providers (N=5/group for a total of 10 providers, 1-hour) will focus on the home BP report experience, with one group of low utilizers and a second group of high utilizers of the electronic health record HBPM reports. Verbal consent for providers interested in focus group participation will be documented in Redcap.

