## **INVESTIGATOR STUDY PLAN – Moms@Home**

### **V1.0**

#### **Describe the data analysis plan, including any statistical procedures**

We will compare HBPM adherence (primary outcome) between the two arms (Moms@Home and ESC). Other outcomes (see section 10) will be compared using generalized estimating equations accounting for the appropriate distribution (e.g., binomial — dichotomous outcome such as HBPM adherence, or Poisson/Negative Binomial — count). We will quantify missing data and dropouts and examine reasons for ineligibility and discontinuation. All data distributions will be examined, and summary statistics calculated by group using an intention-to-treat approach. We will also include other potential modifiers of the intervention effect, potential confounders, and other covariates of interest. In the event of possible effect modification, we will explore the nature of the relationship through the use of interaction terms and subsequent subgroup analysis. This approach will be used for measures with pre-post measurements as well as those collected post-implementation only. Although the pilot study may not have adequate statistical power for testing our hypotheses of improved BP control and medication adherence, we will conduct an exploratory analysis of any treatment effects. We will also examine HBPM adherence by race/ethnicity. Per-protocol analysis will also be performed using all data available from randomized participants without replacement of missing data. Goal attainment scaling, step count, and sleep duration will be characterised for each participant, and then compared between the Moms@Home and ESC groups using a Wilcoxon-Mann-Whitney rank-sum test. In an exploratory analysis, we will compare HBPM, BP control, activity, frequency of visits, and pregnancy outcomes between the primary groups and subgroups (stratified by race/ethnicity, health literacy, income level, age, obesity, and trimester). Qualitative analyses will use applied thematic and content analysis for post-intervention focus groups. All quantitative analyses will be conducted using SAS 9.4 or STATA version 18. We will estimate relevant parameters including estimates of trial retention, intraclass correlation coefficient, standard deviation, and effect size for future R01 power calculations.

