## **22. SETTING**

Subjects will be identified and recruited in the four OB/MFM clinics at UMass Memorial Hospital (mentioned above) from where they are referred and from the UMass Memorial Hospital inpatient service to enroll in the study. Consenting will happen in private rooms at the OB/MFM clinics or in private rooms in the hospital. Subjects will be given adequate time to have all their questions answered and to carefully consider participation. EHR data collection and chart review will be done in the investigators' private offices and in touch-down spaces in the clinic and hospital.

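### Gestational age at delivery is scheduled at baseline, 4 and 8 weeks, when women are 8 to 34 weeks pregnant, and nothing schedules record review through delivery

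*Protocol*

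**What the plan says.** Only the protocol is at hand. These places bear on the point:

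- **Section 10, secondary outcome measures.** One bullet covers healthcare utilisation and "clinical outcome measures (ex. gestational age at delivery, preeclampsia) (baseline, 4, 8 weeks", all under a single schedule.
- **Section 6, inclusion criteria.** "Diagnosis of Chronic hypertension (8-26 weeks gestational age) or gestational hypertension (20-26 weeks gestational age".
- **Section 9.** Each woman's "participation in the study: 8 weeks". Enrolment is expected to take 1.5 years, possibly longer, and the section adds "Estimated timeline for investigators to complete this study: 2 years".
- **Section 11.** "Participant data will be collected at baseline (study entry) and the 8-wk follow-up", with a phone check-in at 4 weeks.
- **Section 10, BP measures.** "Electronic health record review will be used to determine clinic BP values". This is the only outcome in Section 10 for which record review is named as the source.
- **Section 22.** "EHR data collection and chart review will be done in the" investigators' offices and clinic or hospital workspaces. It gives the place, but no period and no outcome.
- **Section 13.** In an exploratory analysis, "we will compare HBPM, BP control, activity, frequency of visits, and pregnancy outcomes between the primary groups and subgroups", with trimester among the subgroup factors.

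**The concern.** Gestational age at delivery exists once per pregnancy, when it ends. The protocol schedules it at three visits during pregnancy. Followed as written, the data set holds no baseline values, and its later values come only from women who delivered before the visit.

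Comparing the recorded values between arms would then be a comparison among early deliveries alone. Whether a woman enters that comparison depends on the outcome and possibly on the arm, so randomisation no longer protects it. The share delivered by week 8 could be compared validly, but that is a different quantity from the one listed.

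Preeclampsia is a lesser matter. A current diagnosis is an exclusion, so new cases up to week 8 can be counted in both arms. But observation ends at a gestation that depends on when the woman entered, so the result describes 8 weeks and not the pregnancy. In the planned trimester subgroups it would describe different stretches of pregnancy.

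**Working it through.** The protocol gives no figure for this outcome to reproduce. Its one computed figure, 43 per arm for 10% versus 35% adherence (two-sided alpha 0.05), does reproduce, with power 0.804. It does not depend on this point.

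**Step 1. Gestation at each scheduled point** = gestation at entry (Section 6) + weeks since entry (Section 10).

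| Point | Chronic hypertension | Gestational hypertension |
|---|---|---|
| Baseline | 8 to 26 weeks | 20 to 26 weeks |
| Week 4 | 8+4=12 to 26+4=30 | 20+4=24 to 26+4=30 |
| Week 8 | 8+8=16 to 26+8=34 | 20+8=28 to 26+8=34 |

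**Step 2. Who has a value.** At baseline, nobody. At week 8, a woman who entered at gestation g has a value only if the pregnancy ended by g+8. That limit is 16 weeks for entry at 8 weeks and 34 weeks for entry at 26 weeks.

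**Step 3. How many.** The protocol states no early-delivery rate, so the rates below are assumptions.

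| Assumed share delivered by week 8 | With a value, of 100 | Average per arm | Without a value |
|---|---|---|---|
| 2% | 2 | 1 | 98 |
| 5% | 5 | 2.5 | 95 |
| 15% | 15 | 7.5 | 85 |

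**Step 4. Time still to run after the week-8 visit** (delivery at 40 weeks assumed). 40−34 = 6 weeks to 40−16 = 24 weeks; for gestational hypertension, 6 weeks to 40−28 = 12 weeks. Counted from entry, this is 40−26 = 14 to 40−8 = 32 weeks, against the 8 weeks of participation in Section 9.

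**Step 5. Does another section extend the window?** Section 11 describes collection at baseline and 8 weeks with a call at 4 weeks. Section 10 ties record review to clinic BP. Section 22 gives no period. Sections 26 and 27 describe record review for prescreening. None of them sets review through delivery.

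**Step 6. Does the study timeline allow it?** 2.0 − 1.5 = 0.5 year, about 26 weeks, remains after the last enrolment.

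- A woman enrolled on the last day reaches 40 weeks within that time if she entered at 40−26 = 14 weeks or later (37−26 = 11 weeks if she delivers at 37).
- If she entered at 8 weeks, she overruns by (40−8)−26 = 6 weeks, or (37−8)−26 = 3 weeks.

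**The case against.** The strongest reply is that this is drafting shorthand. One bullet carries utilisation measures and clinical outcomes under one time tag. The tag fits clinic visits, emergency visits, admissions and preeclampsia, and misfits a single item given as an example. Since Section 13 plans to compare pregnancy outcomes, the investigators presumably mean to obtain them. Chart review needs no active participation, so the 8 weeks in Section 9 need not bound it. Section 11 concerns data collected from the woman herself, and Section 22 allows chart review without an end date. An abstraction window may also sit in a document not shown here.

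Much of this stands. Sections 9, 11 and 22 do not forbid later review. They are silent on it, and the case does not rest on that silence alone. Eight-week incidence of preeclampsia is a legitimate outcome for an 8-week intervention. The item is one example within a secondary outcome, analysed as exploratory in a 100-woman pilot.

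What does not fall away is the stated schedule. Section 10 gives time points for gestational age at delivery, and those time points cannot produce it for women still pregnant. A SAP can define an analysis, but it cannot supply data that the protocol does not schedule. Leaving staff to look up deliveries informally risks uneven ascertainment and leaves consent coverage unchecked.

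Section 6 could also be read as gestation at diagnosis rather than at entry. That would shift the 16 to 34 week range. Baseline values would still be impossible, and follow-up to delivery would still be unscheduled.

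**Conclusion.** The concern holds. As scheduled, gestational age at delivery has no baseline value for anyone. At week 8 it has a value only for women already delivered, at about 34 weeks or earlier, so the planned comparison between arms cannot validly be made for it. Under assumed early-delivery rates of 2% to 15%, 85 to 98 of 100 women lack a value. The conclusion is the same at any rate in that range.

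Preeclampsia remains comparable between arms as incidence over 8 weeks from entry, but should not be read as incidence over the pregnancy. The HBPM adherence outcome and the sample size are untouched. This should be corrected, but it does not threaten the trial's main aim.

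The 16 to 34 week range assumes that the Section 6 windows describe gestation at entry. The timing figures assume delivery at 37 to 40 weeks.

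**What to change.** **Preferred.** In Section 10, keep baseline, 4 and 8 weeks for the utilisation measures and give gestational age at delivery its own source and time: health record review through delivery for all randomised women. Record preeclampsia through delivery in the same abstraction. State this review window in Section 9, separately from the 8 weeks of active participation, and check that the consent form covers it.

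**Alternative.** If follow-up to delivery is not wanted, remove gestational age at delivery from Section 10 and label preeclampsia as incidence from entry to week 8.

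**Cost.** The preferred change needs one later chart abstraction per woman, 6 to 24 weeks after her week-8 visit (delivery at 40 weeks assumed), plus timeline and consent wording. It adds no visits. The roughly 26 weeks after planned enrolment cover most late entrants, but a woman entering at 8 weeks at the very end of accrual would deliver 3 to 6 weeks after the planned study end. A few delivery records may therefore follow the main result. The margin shrinks if enrolment runs beyond 1.5 years, and final analysis must fit in the same half-year. The alternative costs only a wording change, but gives up the delivery outcome.

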## INVESTIGATOR STUDY PLAN – Moms@Home

### V1.0

- N/A

Secondary safety endpoints

- N/A

The primary outcome measures will be assessed using the Observed vs Expected number of HBPM readings recorded for participants over the study period. Group comparison will be done between the Moms@Home group vs ESC group.

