#### **Study arms:**

**Moms@Home intervention arm:** Participants randomized to Moms@Home will receive the Moms@Home app ( $\pm$  Samsung smartphone), the digital BP monitor and cuff, and FitBit activity tracker. An orientation, FAQ sheet and HBPM pamphlets will include HBPM instructions, safety protocols, an introduction to the app, and tech support for the digital BP monitor, app, and FitBit. The FAQ sheet and HBPM pamphlet will be generated and submitted through a later modification of the IRB for approval before use. Participants randomized to the Moms@Home intervention arm will be helped by research staff to download and set up the MDH app and will be provided with a Bluetooth enabled blood pressure cuff and a FitBit that syncs with MDH .

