## **INVESTIGATOR STUDY PLAN – Moms@Home**

### **V1.0**

Participants in the Moms@Home arm who do not have a smartphone, or have a limited data plan and prefer a study phone will be provided with a study smartphone, which they will return after their time on the study. Participants will each select personalization for daily notifications and set one personal goal. Participants will also be reminded to take daily home blood pressure measurements to be synced into the app.

**Enhanced Standard Care (ESC) arm:** Participants randomized to Enhanced Standard Care (ESC) will receive the digital BP monitor and cuff, a paper diary to record BP values, and a FitBit activity tracker. A modified orientation and FAQ sheet will include the same HBPM instructions, safety protocols, and tech support for the digital BP monitor and FitBit. Participants will each set one personal goal. Participants will also be reminded to take daily home blood pressure measurements to be recorded in the paper diary.

At home, over the 8-week RCT, participants will be instructed to measure their BP daily (2 readings, separated by 1 min) after a 3 min rest period. An HBPM video for reference will be part of the Moms@Home portal. The Moms@Home portal can be programmed with English or Spanish as default language and all videos will have Spanish subtitles. Traffic light (red, yellow, green) alerts and actions for abnormal BP values will be reviewed using a teach-back method. Participants will also be instructed to wear the study FitBit for daily activity and heart rate monitoring. Data from the FitBit will be transmitted through the MDH app to the study team for participants randomized to the intervention arm. For participants who are randomized to the enhanced standard care arm, de-identified physical activity i.e. daily steps, heart rate data and sleep data will be collected via encrypted methods through the FitBit app. Staff will be able to confirm data transmission prior to the participant heading home. The research team will call participants 1–3 days after their scheduled start to address any concerns, ensure data capture, and provide tech support.

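### Primary adherence is counted from app syncs in one arm and a paper diary in the other, so recording method coincides with arm

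*Protocol*

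**What the plan says.** Hypothesis 1 (protocol section 4) is about behaviour: intervention participants "will have better adherence to HBPM, compared to participants in the control ESC group at 8 weeks". Section 10 turns this into a count: "The primary outcome measures will be assessed using the Observed vs Expected number of HBPM readings recorded for participants over the study period". That sentence does not say where the readings come from.

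Section 11 describes one recording route per arm:

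- **Moms@Home.** Participants are "provided with a Bluetooth enabled blood pressure cuff and a FitBit that syncs with MDH", the study app. The instruction is: "Participants will also be reminded to take daily home blood pressure measurements to be synced into the app".
- **ESC.** Participants "will receive the digital BP monitor and cuff, a paper diary to record BP values, and a FitBit activity tracker". The instruction is: "Participants will also be reminded to take daily home blood pressure measurements to be recorded in the paper diary".

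Section 10 names the same two sources under the secondary BP measures: "HBPM measures will be gathered from the Moms@Home app and paper BP diaries". The electronic record is used there for clinic BP only. Electronic capture for ESC through the FitBit app covers steps, heart rate and sleep, not BP (section 11). Monitors are returned at 8 weeks in both arms (section 24), but nothing is said about reading their memory.

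**The concern.** Recording method is fully aligned with randomized arm, and the two routes fail in different ways. A diary entry can be filled in later without a measurement, a real measurement can go unlogged, and a diary can be lost. An app reading can fail to sync. Randomization balances participants; it does not balance two measuring instruments assigned one to each arm.

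The error can go either way. Back-filled diaries or failed syncs could hide a real effect. Unlogged readings or lost diaries in ESC could inflate an apparent one or create one. Section 13 also passes the effect size on to the power calculation for the future R01, so any error would be carried into the design of the larger trial.

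**Working it through.** **The plan's own figure.** Section 13 uses a two-sided chi-square test, alpha 0.05, 10% vs 35%, 80% power, 43 per arm. With the pooled-variance formula and mean proportion 0.225:

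n = [1.960 × √(2 × 0.225 × 0.775) + 0.842 × √(0.10 × 0.90 + 0.35 × 0.65)]² / 0.25² = 42.6, rounded up to 43.

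The sample size reproduces (approximate power 80.4%) and is not in dispute.

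**Expected readings.** Two a day over 8 weeks: 2 × 7 × 8 = 112 per participant.

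**Illustration of recording error.** The documents give no rate of back-filling, loss or failed sync, so every error rate below is an assumption. The 10% and 35% are taken as true adherence. Rejection rates come from exact enumeration of two binomials with the uncorrected chi-square test at two-sided 0.05.

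Formulas for the observed proportions:

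- ESC with fraction b of non-adherers appearing adherent: 0.10 + b × 0.90
- Moms@Home with fraction m of adherers lost: 0.35 × (1 − m)
- ESC with both errors: 0.10 × (1 − m) + 0.90 × 0.05

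| Scenario (true 10% vs 35%) | Observed ESC vs Moms@Home | Difference | Power, 43/arm | Power, 50/arm |
|---|---|---|---|---|
| No recording error | 10% vs 35% | 25 points | 0.827 | 0.877 |
| (a) b = 5% in ESC | 14.5% vs 35% | 20.5 | 0.617 | 0.677 |
| (a) b = 10% in ESC | 19% vs 35% | 16 | 0.395 | 0.443 |
| (b) m = 10% in Moms@Home | 10% vs 31.5% | 21.5 | 0.723 | 0.784 |
| (b) m = 20% in Moms@Home | 10% vs 28% | 18 | 0.593 | 0.659 |
| Offsetting in ESC: b = 5%, m = 20% | 12.5% vs 35% | 22.5 | 0.716 | 0.775 |
| Offsetting in ESC: b = 5%, m = 30% | 11.5% vs 35% | 23.5 | 0.763 | 0.819 |

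With no true effect, both arms have true adherence p and the observed rate in an arm is p × (1 − m). False-positive rates at 43 per arm (50 per arm in brackets):

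| Adherers missed | p = 10% | p = 35% |
|---|---|---|
| None | 0.059 (0.051) | 0.054 (0.049) |
| 20% in ESC only | 0.072 (0.062) | 0.111 (0.115) |
| 20% in ESC, 10% in Moms@Home | 0.063 (0.051) | 0.067 (0.067) |
| 20% in both arms | 0.060 (0.047) | 0.052 (0.050) |

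The false-positive rate stays close to its no-error value when both arms lose the same fraction. It rises when they differ. A common recording source is meant to remove that difference.

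**The case against.** The best counter-argument is that the difference in routes belongs to the comparison. Section 4 defines the comparator as a monitor plus diary, and an app that makes capture easier is arguably part of the intervention. On that view a difference in recorded readings is a legitimate pragmatic target. This stands as far as it goes, but the claim is then about recorded readings, whereas Hypothesis 1 is about adherence to home monitoring. Either the source or the claim has to change.

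Second, the primary-outcome sentence names no source, and a source rule could sit in a document not shown. This lowers confidence. It does not remove the point, because the diary is the only route described for ESC and a later analysis plan cannot create a common source after data collection.

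Third, there are safeguards: a staff check of data transmission before participants go home (its application to BP is unclear), a call 1–3 days after the start, a 4-week phone check-in, twice-daily viewing of the platform for abnormal values, and data checks that include bias detection (sections 11, 13 and 14). These may reduce the error, and digit-preference checks may flag invented entries. None recovers an unlogged reading or gives a source common to both arms. Blinded assessors do not help, because the error arises at capture.

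Fourth, the size is not anchored. The error rates are assumed, no cut-off for being adherent is given, and offsetting errors shrink the effect. If the prior-work rates in section 13 already include recording error, part of the power loss disappears. All of this stands and limits what can be said about size.

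Finally, monitor return may differ by arm, and counting unreturned monitors as non-adherent would discard app readings already captured. That is a real cost of the remedy and needs a sensitivity analysis.

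**Conclusion.** The concern holds. As written, recording error is tied to arm on a primary outcome, and the comparison cannot distinguish measuring from capture. The structural problem is clear from the text, on the assumption that no common source is set out in a document not shown. Its net direction and size are unknown. Under the assumed error rates, power at 43 per arm lies between 40% and 76%, against 83% without error. With no true effect and unequal loss, the false-positive rate lies between 6.3% and 11.1%, against 5.9% and 5.4% without error. These figures show sensitivity and are not estimates. The point should be fixed before enrolment, even in a pilot, because the outcome is formally tested and its effect size feeds the next trial.

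**What to change.** 1. Before enrolment, confirm whether the issued monitors store about 112 date-stamped readings. The protocol does not say.
2. If they do, define the primary adherence count in both arms from monitor memory, downloaded when the monitor is returned at 8 weeks. Keep app and diary counts as secondary sources and report their agreement with the monitor by arm.
3. Apply one rule for unreturned monitors in both arms, for example counted as non-adherent. Add a sensitivity analysis leaving them out, and report return rates by arm.
4. If the memory is inadequate, state in sections 4 and 10 that the primary outcome is recorded (captured) readings and limit the conclusion to that. Report whatever monitor-stored readings are available as a check on app and diary counts by arm.

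**Cost.** Protocol wording, one check of the devices, and staff time for one download per returned monitor (up to about 100). No extra participants or visits are needed: both arms already receive a monitor, and the final stipend already depends on returning it. The downside is data lost through unreturned monitors, possibly unequally by arm. If the memory is inadequate, the cost is wording and a partial check only.
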